## **6.2           IMPORTANT PROTOCOL DEVIATIONS**

Consistency check listings (for identification of deviations from time windows) and a list of protocol deviations (e.g. deviations in drug administration, in blood sampling times, etc.) will be provided to be discussed at the Report Planning Meeting (RPM). At this meeting, it will be decided whether a discrepant data value can be used in analyses or whether it must be corrected in the clinical database. Each protocol deviation must be assessed to determine whether it is an important PD (IPD). For definition of IPDs, and for the process of identification of these, refer to the BI reference document "Identify and Manage Important Protocol Deviations (IPD)" [\(2\)](#).

If any IPDs are identified, they are to be summarised into categories and will be captured in the decision log. Categories which are considered to be IPDs in this trial are defined in the integrated quality and risk management plan (IQRMP). If the data show other IPDs, the definition in the IQRMP will be supplemented accordingly by the time of the RPM.

IPDs will be summarized and listed. Which kind of IPDs could potentially lead to exclusion from which analysis set is specified in the DV domain template. The decision on exclusion of subjects from analysis sets will be made at the latest at the RPM, after discussion of exceptional cases and implications for analyses. If the data show other IPDs, this table will be supplemented accordingly by the time of the RPM.

Non-important COVID-19 related PDs will only be listed.

## 6.3 SUBJECT SETS ANALYSED

### Section 7.3 of the CTP:

[...]

*Statistical analyses will be based on the following analysis sets:*

- *Treated set (TS): The treated set includes all subjects who were randomised (SRD and MD part) / allocated (DDI part) and treated with at least one dose of trial drug. The treatment assignment will be determined based on the first treatment the subjects received. The treated set will be used for safety analyses.*
- *Pharmacokinetic parameter analysis set (PKS): This set includes all subjects in the treated set (TS) who provide at least one primary or secondary PK endpoint that was not excluded due to a protocol deviation relevant to the evaluation of PK or due to PK non-evaluability (as specified in the following subsection 'Pharmacokinetics'). Thus, a subject will be included in the PKS, even if he contributes only one primary or secondary PK parameter value for one period to the statistical assessment. Descriptive and model-based analyses of PK parameters will be based on the PKS.*

[...]

*Plasma and urine concentration data and parameters of a subject will be included in the statistical pharmacokinetic (PK) analyses if they are not flagged for exclusion due to a protocol deviation relevant to the evaluation of PK (to be decided no later than in the Report Planning Meeting) or due to PK non-evaluability (as revealed during data analysis, based on the criteria specified below). Exclusion of a subject's data will be documented in the CTR.*

*Relevant protocol deviations may be*

- *Incorrect trial medication taken, i.e. the subject received at least one dose of trial medication the subject was not assigned to*
- *Incorrect dose of trial medication taken*
- *Use of restricted medications*

[figure not shown]
*Plasma and urine concentrations and/or parameters of a subject will be considered as non-evaluable, if for example*

- *The subject experienced emesis that occurred at or before two times median  $t_{max}$  of the respective treatment (Median  $t_{max}$  is to be determined excluding the subjects experiencing emesis),*
- *Missing samples/concentration data at important phases of PK disposition curve*
- *A predose concentration of BI 1323495 is  $>5\%$   $C_{max}$  value of that subject in the respective treatment period (only DDI part).*

The descriptive analysis of PK concentrations and endpoints will be based on the ADS ADPC and ADPP, respectively, as described at the beginning of [Section 7](#).

Table 6.3: 1 Subject sets analysed

Class of endpoint	Subject set	
	TS	PKS
Analyses of PK endpoints		X
Analyses of PD endpoint	X	
Safety parameters	X	
Demographic/baseline parameters	X	
Important protocol deviations	X	
Disposition	X	
Treatment exposure	X	

## 6.5 POOLING OF CENTRES

This section is not applicable, because the study was performed in only one centre.

## 6.6 HANDLING OF MISSING DATA AND OUTLIERS

### Section 3.3.4 of the CTP:

*If a subject is removed from or withdraws from the trial prior to the first administration of trial medication, the data of this subject will not be entered in the case report form (CRF) and will not be reported in the clinical trial report (CTR). If a subject is removed from or withdraws from the trial after the first administration of trial medication, this will be documented and the reason for discontinuation must be recorded in the CRF; in addition, the data will be included in the CRF and will be reported in the CTR.*

### Section 7.5.1 of the CTP:

*It is not planned to impute missing values for safety parameters.*

One exception where imputation might be necessary for safety evaluation is AE dates. Missing or incomplete AE dates are imputed according to BI standards [\(3\)](#).

Missing data and outliers of PK data are handled according to BI standards (see [\(4\)](#) and [\(5\)](#)).

**Section 7.5.2 of the CTP:**

*PK parameters that cannot be reasonably calculated based on the available drug concentration-time data will not be imputed.*

**6.7 BASELINE, TIME WINDOWS AND CALCULATED VISITS**

The baseline value is defined as the last measurement before administration of BI 1323495 in each treatment period.

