mode of admin.	SRD and MD part: Oral with 240 mL of water after a standardized meal DDI part: Oral with 240 mL of water after an overnight fast of at least 10 h
Test product 2 (Only for DDI part)	Itraconazole oral solution (ITRIZOLE® Oral Solution 1% [REDACTED])
dose	200 mg q.d.
mode of admin.	Oral with 240 mL of water after an overnight fast of at least 9 h
Comparator products: (Only for SRD part)	Matching placebo tablets
dose:	Not applicable
mode of admin.:	Oral with 240 mL of water after a standardized breakfast
Duration of treatment	SRD part: Single dose 1 day MD part: 30 mg bid; 11 days, 10 days twice daily (bid) dosing and single dose on day 11 60 mg qd; Once daily, multiple doses over 11 days DDI part: Treatment R (BI 1323495 alone): Single dose of 10 mg BI 1323495 (Day 1) Treatment T (itraconazole + BI 1323495): 10 days of itraconazole treatment (200 mg itraconazole once daily from Day -3 to Day 7) combined with a single dose of 10 mg BI 1323495 on the fourth day of the itraconazole treatment (Day 1, 1 h after the itraconazole administration) Wash-out period: Administrations of BI 1323495 will be separated by a wash-out phase of at least 11 days

Proprietary confidential information © 2021 Boehringer Ingelheim International GmbH or one or more of its affiliated companies

Statistical methods	
SRD and MD part: Descriptive statistics will be calculated for all endpoints.
 
DDI part: Relative bioavailability will be estimated by the ratios of the geometric means (Treatment T/Treatment R) for the primary and secondary endpoints. Additionally, their two-sided 90% confidence intervals (CIs) will be provided. This method corresponds to the two one-sided t-test procedure, each at a 5% significance level. Since the main focus is on estimation and not testing, a formal hypothesis test and associated acceptance range are not specified. The statistical model will be an analysis of variance (ANOVA) on the logarithmic scale including effects for 'subject' and 'treatment'. CIs will be calculated based on the residual error from the ANOVA.
 
Descriptive statistics will be calculated for all endpoints.

----------------------------	---

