Period 2/Treatment T (BI 1323495 + itraconazole) 	3	-3	-72:00	09:00	Ambulatory visit, itraconazole administration	x B,2,3			x			x 
		-2	-48:00	09:00	Ambulatory visit, itraconazole administration							x 
		-1	-24:00	09:00	Ambulatory visit, itraconazole administration 	x C,2,3		x 				x 
			-12:00	21:00	Admission to trial site 							
	1 		-2:00	07:00			x 		x 	x 	x 	x 
			-1:00	08:00	Itraconazole administration			x 				
			0:00	09:00	BI 1323495 administration							
			0:20	09:20			x					
			0:40	09:40			x					
			1:00	10:00			x					
			1:30	10:30			x					
			2:00	11:00	240 mL fluid intake		x					
			3:00	12:00			x					
			4:00	13:00	240 mL fluid intake, thereafter lunch 		x		x	x	x	
			5:00	14:00			x					
			6:00	15:00			x					
			7:00	16:00	Snack (voluntary) 		x					
			8:00	17:00			x					
			9:00	18:00			x					
			10:00	19:00	Dinner 		x					
			12:00	21:00			x					x
	2		23:00	08:00	Itraconazole administration	x B,2						x
			24:00	09:00	Breakfast (voluntary) 		x		x	x	x	
			28:00	13:00	Lunch (voluntary)							
			31:00	16:00	Snack (voluntary)							x
			34:00	19:00	Discharge from trial site		x					x
	3		47:00	08:00	Ambulatory visit, itraconazole administration		x 	x 				x
			71:00	08:00	Ambulatory visit, itraconazole administration	x C,2	x 					x
	4		95:00	08:00	Ambulatory visit, itraconazole administration		x 					x
			119:00	08:00	Ambulatory visit, itraconazole administration	x C,2	x 					x
			143:00	08:00	Ambulatory visit, itraconazole administration		x 	x 				x
			167:00	08:00	Ambulatory visit	x B	x	x				x
EOT	4	16 to 23			End of trial (EOT) examination 	x A			x	x	x	x

Clock time should be adjusted based on actual administration time

1. Subject must be informed and written informed consent obtained prior to starting any screening procedures. Screening procedures include medical examination, check of vital signs, ECG(12-lead ECG), chest x-ray, safety laboratory (including drug screening), pharmacogenetic analysis for UGT2B17 genotype, demographics (including determination

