Proprietary confidential information © 2021 Boehringer Ingelheim International GmbH or one or more of its affiliated companies

of body height and weight, smoking status and alcohol history), relevant medical history, concomitant therapy and review of inclusion/exclusion criteria.

2. The time is approximate; the procedure is to be performed and completed within the 3 h prior to drug administration.
3. Urine drug screening and alcohol breath test
4. If several actions are indicated at the same time, the intake of meals will be the last action.
5. Letters A, B and C define different sets of safety laboratory examinations (for details refer to Section [5.2.3](#))
6. At the end of trial visit the EOT examination includes medical examination, vital signs, ECG, safety laboratory, recording of AEs and concomitant therapies.
7. AEs and concomitant therapies will be recorded throughout the trial, but will be specifically asked for at the times indicated in the [Flow Chart](#) above.
8. Administration of BI 1323495 in treatment R and T will be separated by at least 11 days.
9. Blood collection takes place at the indicated times. Itraconazole will be administered immediately thereafter.
10. For allowed deviation from the scheduled time please refer to Section [6.1](#).
11. Axillary temperature measurement will be conducted during Day -1.
12. PGx samples will be collected during Day 1.

Proprietary confidential information © 2021 Boehringer Ingelheim International GmbH or one or more of its affiliated companies

MD part (30 mg bid)

Visit	Day	Planned time (relative to first drug administration [h:min])	Approximate clock time of actual day [h:min]	Event and comment	Safety laboratory 		PK blood 	PK urine 	PD blood (NE activity)	12-lead ECG 	Medical examination	Vital signs 	Questioning for AEs and concomitant therapy 
1	-28 to -8			Screening (SCR)  including pharmacogenomics test UGT2B17	x A					x	x	x	
2 	1 	-1	-16:00	17:00 Admission to trial site	x B, 6, 10, 11							x	
			-01:00	08:00 Allocation to treatment 	x C,12	x 	x 	x 	x 	x 	x 	x 	
			-00:30	08:30 breakfast									
			00:00 09:00	First drug administration 			▲						
			00:20	09:20		x	—						
			00:40	09:40		x	—						

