The healthy subject population of this study, as defined by the in- and exclusion criteria, is not affected by any clinically relevant concomitant diseases that might put them at an increased risk of experiencing a severe clinical course of COVID-19 in case of SARS-CoV-2 infection.

Based on these considerations, the benefit/risk assessment for the administration of BI 1323495 to healthy subjects remains unaltered also in face of the COVID-19 pandemic.

*Risk mitigation:*

Ensure that the general measures implemented by the government to control the spread of COVID-19 in the Japanese population are adhered to. COVID-19 infection testing such as PCR test will be conducted before hospitalization.

Itraconazole

In this trial itraconazole will be used in a standard clinical dose of 200 mg once daily for 10 days. Multiple dosing of 200 mg itraconazole up to 15 days was of acceptable tolerability in healthy subjects ([c02336088](#), [c03355329](#), [c08928447](#), [R17-3742](#)). Addition to this, BI 1323495 will not have potential to be CYP3A4 inhibitor.

For a detailed description of the potential risks of itraconazole treatment, please refer to the package insert for ITRIZOLE® Oral Solution 1% ([R20-1269](#)).

Proprietary confidential information © 2021 Boehringer Ingelheim International GmbH or one or more of its affiliated companies

In order to address the risk of hepatotoxicity, only subjects with normal liver enzyme values will be included into the trial. Safety laboratory parameters will be monitored closely.

An individual subject will discontinue the treatment if the subject shows an elevation of AST and/or ALT  $\geq 3$ -fold ULN combined with an elevation of total bilirubin  $\geq 2$ -fold ULN (measured in the same blood sample, see Section [3.3.4.1](#)).

Further, most of the reported cases of serious hepatotoxicity during itraconazole treatment occurred in patients that suffered from concomitant liver diseases, had other significant diseases, or took concomitant hepatotoxic drugs. Subjects with liver diseases or a medical history of drug-induced liver failure are excluded from trial participation.

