**Table 4.1.4: 3 Dosage and treatment schedule in the DDI part**

Treatment period	Treatment	Substance	Formulation	Unit strength	Dosage	Total dose
1	R (Reference)	BI 1323495	Tablet, film-coated	10 mg	1 tablet as single dose (Day 1)	10 mg
2	T (Test)	BI 1323495	Tablet, film-coated	10 mg	1 tablet as single dose (Day 1)	10 mg
		Itraconazole	Oral solution	10 mg/mL	20 mL (200 mg) qd for 10 days (Days -3 to 7)	2000 mg

Table 4.1.4: 4 BI 1323495 and placebo treatments, tablets of MD part for PM

Dose group	Substance	Pharmaceutical form	Unit strength	Number of units per administration	Total daily dose of BI 1323495
1	BI 1323495	Tablet, film-coated	10 mg	3 tablets bid*	60 mg
1	Placebo	Tablet, film-coated	--	3 tablets bid*	--
2	BI 1323495	Tablet, film-coated	10 mg 50 mg	1 tablet each qd	60 mg
2	Placebo	Tablet, film-coated	--	1 tablet each qd	60 mg

\*On Day 11, Subjects will receive a single dose in the morning only. On all other trial days, BI 1323495 will be administered bid.

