Follow-up	Placebo F/U SRD PM 10 mg, F/U SRD PM 30 mg, F/U SRD PM 100 mg, F/U SRD EM 30 mg, F/U SRD EM 70 mg, F/U SRD EM 150 mg, F/U MD PM 30 mg BID, F/U MD PM 60 mg QD, respectively	Date/time of last administration of BI 1323495 or placebo + REP (7 days, i.e., 7 * 24 h)	12:00 a.m. on day after last contact date

 See [Section 6.7](#) for definition of baseline, which will be used in the statistical analyses of safety laboratory data, ECG and vital signs.

For the DDI part of this trial, the following separate phases will be defined for the analyses of AEs:

Table 6.1: 2 Analysis phases and labels for statistical analyses in DDI part

Study analysis phase	Label	Start	End
Screening 	Screening	Date of informed consent	Date/time of first administration of study drug
On treatment: BI Treatment	DDI BI	Date/time of first administration of BI 1323495 or placebo	Date/time of first administration of BI 1323495 + REP (7 days, i.e., 7 * 24 h)
On treatment: Itraconazole (ITZ)	DDI ITZ	Date/time of first administration of itraconazole	Date/time of BI 1323495 administration in treatment period 2 or alternatively, 0:00h on the day after trial termination date in case of no further treatment
On treatment- BI+ ITZ	DDI BI+ITZ	Date/time of BI 1323495 administration in treatment period 2	Date/time of last administration of itraconazole + REP (9 days, i.e., 9 * 24 h) or 12:00 a.m. on day after last contact date (whichever occurs first)
Follow-up BI	F/U DDI BI	End of DDI BI treatment phase (i.e. Date/time of first administration of BI 1323495 + REP (7 days, i.e., 7 * 24 h))	First drug administration of itraconazole or alternatively, 0:00h on the day after trial termination date in case of no further treatment
Follow-up BI	F/U DDI BI+ITZ	End of DDI BI+ITZ treatment phase (i.e. Date/time of last administration of itraconazole + REP (9 days, i.e., 9 * 24 h))	until 0:00h on the day after trial termination date

 See [Section 6.7](#) for definition of baseline, which will be used in the statistical analyses of safety laboratory data, ECG and vital signs.

Two types of AE displays will be provided in the report:

A. Section 15.3 and Appendix 16.1.13.1.8 (only for ClinicalTrials.gov and EudraCT) of the CTR displays:

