## **7.8.2      Laboratory data**

The analyses of laboratory data will be descriptive in nature and will be based on BI standards "Display and Analysis of Laboratory Data" ([9](#)).

Analyses will be based on normalised values, which means transforming to a standard unit and a standard reference range. The original values will be analysed if the transformation into standard unit is not possible for a parameter.

Descriptive statistics of laboratory values over time and for the difference from baseline (see [Section 6.7](#)) will be provided. Frequency tables of changes between baseline and last value on treatment with respect to the reference range will be presented.

Unscheduled measurements of laboratory data will be assumed to be repeat measurements of the most recent scheduled measurement (e.g. for follow-up or confirmation of a particular value). Therefore, unscheduled measurements will be assigned to the planned time point of the previous scheduled measurement. Descriptive statistics will be calculated by planned time point based on the worst value of the subject at that planned time point (or assigned to that planned time point).

Possibly clinically significant abnormal laboratory values are only those identified either in the Investigator's comments or at the Report Planning Meeting at the latest. It is the Investigator's responsibility to decide whether a lab value is clinically significant abnormal or not. Standard or project-specific rules for flagging clinically significant values in an automated manner will not be applied in this study.

Clinically relevant findings in laboratory data will be reported as baseline conditions (prior to first administration of study treatment) or as AEs (after first administration of study treatment) if judged clinically relevant by the investigator, and will be analysed as such.

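### In DDI Period 2 the SAP baseline follows two itraconazole doses for liver enzymes and three for vital signs, but none for bilirubin, creatinine and haematology

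*SAP*

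**What the plan says.** SAP 6.7 defines baseline in one sentence: "The baseline value is defined as the last measurement before administration of BI 1323495 in each treatment period". The footnotes to SAP Tables 6.1: 1 and 6.1: 2 point to it as the "definition of baseline, which will be used in the statistical analyses of safety laboratory data, ECG and vital signs".

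SAP 7.8.2 plans "Descriptive statistics of laboratory values over time and for the difference from baseline", and also tables of shifts against the reference range from baseline to the last on-treatment value. SAP 7.8.3 plans differences from baseline for vital signs. Protocol 7.3.4 compares Treatment T with Treatment R descriptively for safety.

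On the schedule, the Protocol synopsis places BI 1323495 in Treatment T "on the fourth day of the itraconazole treatment (Day 1, 1 h after the itraconazole administration"). Protocol Table 4.1.4: 3 gives itraconazole as "20 mL (200 mg) qd for 10 days (Days -3 to 7"). In the DDI flow chart, Days -3, -2 and -1 of Period 2 each read "Ambulatory visit, itraconazole administration". Footnote 2, attached to the pre-dose assessments, states that "the procedure is to be performed and completed within the 3 h prior to drug administration".

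**The concern.** Treatment T is itraconazole plus BI 1323495. A baseline tied to BI 1323495 alone falls part-way through the itraconazole course for whatever is measured on Day -1 or Day 1, and before the course for whatever was last measured on Day -3. The same rule therefore gives different kinds of baseline within one laboratory table. In Period 1 the corresponding values are taken before any drug.

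The parameters that shift include the transaminases. Protocol 1.4.2, under itraconazole, says: "In order to address the risk of hepatotoxicity, only subjects with normal liver enzyme values will be included into the trial". Transaminases and bilirubin are also judged together in the hepatic injury definition (Protocol 5.2.6.1.4), yet their Period 2 changes would be measured from different starting points. A reader of the T versus R change tables would not be told this.

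**Working it through.** **1. Reproduce the plan's schedule.** Itraconazole times in the DDI flow chart, in hours relative to BI 1323495 in Period 2, are -72, -48, -24, -1, 23, 47, 71, 95, 119 and 143. That is 10 doses, and 10 × 200 mg = 2000 mg, as in Protocol Table 4.1.4: 3. Four of them (-72, -48, -24, -1) precede BI 1323495, which agrees with the synopsis placing it on the fourth itraconazole day.

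**2. Find the last scheduled value before BI 1323495.** Protocol Table 5.2.3: 1 shows that set C holds only AST, ALT, alkaline phosphatase and GGT. Set B holds those four plus bilirubin, creatinine, haematology and others. Footnote 2 puts the Day -3 and Day -1 samples before that day's dose.

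| Parameter | Baseline under SAP 6.7, Period 2 | Earlier itraconazole doses |
|---|---|---|
| AST, ALT, alkaline phosphatase, GGT | set C, Day -1 (-24 h) | 2 (-72, -48) |
| Vital signs | Day 1, -2 h | 3 (-72, -48, -24) |
| Bilirubin, creatinine, haematology | set B, Day -3 (-72 h) | 0 |

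If the Day -1 sample were taken after the dose, the enzyme count would be 3. If the Day 1 three-hour window is read relative to BI 1323495 and the measurement is taken after -1 h, the vital-sign count would be 4. Neither reading gives 0.

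**3. Effect on the change tables.** For one subject in Treatment T, let Y0 be the value before the first itraconazole dose, Yb the last value before BI 1323495, and Yt a later value. Then:

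- difference under SAP 6.7 = Yt − Yb
- difference from the untreated value = Yt − Y0
- gap between the two = Yb − Y0 = L, the change during the itraconazole lead-in.

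In Treatment R both references are drug-free, so there is no such term. For enzymes and vital signs, the T minus R contrast of mean changes under SAP 6.7 equals the contrast from untreated baselines minus the mean of L. For enzymes this applies at every later Period 2 sample (23, 71, 119 and 167 h). For bilirubin, creatinine and haematology Yb = Y0, so nothing is removed. The documents give no value for L.

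**4. Effect on the shift tables.** Exclusion criterion 28 bars subjects with ALT, AST or GGT above the upper limit of normal at screening. If one of these rises above the limit by Day -1 of Period 2, it is tabulated as already high at baseline, and the move from normal to high does not appear.

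**5. Is Day -3 a clean reference?** BI 1323495 doses are at least 11 days apart: 11 × 24 = 264 h, and 264 − 72 = 192 h = 8 days. The Day -3 sample is therefore at least 8 days after the Period 1 dose, beyond the 7-day residual effect period in Protocol 1.2.3.

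**6. Against the SAP's own phases.** SAP Table 6.1: 2 treats the time from first itraconazole to BI 1323495 as an on-treatment itraconazole phase. The enzyme and vital-sign baselines lie inside that phase.

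**The case against.** The best defence is that a baseline before BI 1323495 in each period answers a sensible question: what changes once BI 1323495 is given, alone or on an itraconazole background. It matches the combined AE phase, which starts at BI 1323495. That stands as a reason to keep the value. It does not explain why bilirubin, creatinine and haematology start from an untreated value, and the SAP does not state this purpose.

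It is also fair that little can be hidden. The hepatic injury definition and the matching discontinuation criterion use multiples of the upper limit of normal. Values over time are summarised, individual values are listed, and AEs on itraconazole alone have their own phase. In trial 1405-0009, which gave the same combination to extensive metabolizers, Protocol 1.2.1 reports no relevant laboratory, vital-sign or ECG changes. All of this limits the consequence; none of it removes the inconsistency.

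Three stronger readings are tempting, and the documents do not support them:

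- **That T versus R is biased toward no difference.** This needs the lead-in change and the later change to have the same sign. With opposite signs, the planned baseline can enlarge the apparent change in T.
- **That ECG results are distorted.** The Day 1 ECG does follow three doses, but SAP 7.8.4 plans no change-from-baseline summary.
- **That placebo subjects have no baseline.** Read literally, SAP 6.7 omits the 3×2 + 3×1 + 2×3 = 15 placebo subjects among the 60 planned for SRD and MD. SAP Table 6.1: 1 names placebo alongside BI 1323495 and sends the reader to 6.7, so the intent is clear and the gap is editorial.

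**Conclusion.** The point holds as a matter of analysis definition. For all 14 planned DDI subjects, the Period 2 baseline is on itraconazole for four liver enzymes (two doses) and vital signs (three doses), and untreated for bilirubin, creatinine and haematology. The tables affected are the difference-from-baseline summaries for enzymes and vital signs and the reference-range shifts for the enzymes. Their T versus R contrast is displaced by the lead-in change, whose size and direction are unknown.

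The consequence is confined to descriptive safety tables. The PK endpoints, the AE analyses, the AESI rule based on the upper limit of normal, and ECG are not affected. The dose counts assume nominal times, footnote 2 as printed, and the flow-chart columns as they appear in the text. The change is worth making because it is cheap and the planned tables would otherwise be hard to interpret.

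**What to change.** In SAP 6.7:

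- **Laboratory data, DDI Period 2.** Define baseline as the last value before the first itraconazole dose. This is the Day -3 set B sample, which already contains all four enzymes, so no new sample is needed. Report the last value before BI 1323495 as a second, labelled reference for the change after BI 1323495 is added.
- **Vital signs, DDI Period 2.** The flow chart's vital-signs column shows no entry before itraconazole, but Day -3 appears to carry a medical examination, and Protocol 5.2.1 says that includes a review of vital signs. If a value is recorded there before the dose, use it. If not, keep the value before BI 1323495, label it as on itraconazole, and show the change from the Period 1 pre-dose value as supplementary only. That value is at least 8 days older than the first itraconazole dose, so it should not become the main baseline.
- **SRD and MD.** Add placebo to the definition alongside BI 1323495, as SAP Table 6.1: 1 already does.

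The cost is a short rewording of SAP 6.7, one extra derived baseline variable and extra columns in the DDI safety tables.
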